### **8.11 Revisions, Replacements, or Explants (Additional Surgery)**

The subject and the implanting physician will collectively make the decision about any possible revision of the device based upon what is medically safe, what is desired by the subject, and what is in the subject's best medical interests. Any system revision, replacement or explant will be recorded on the appropriate eCRFs. If the device is explanted for any reason and re-implantation is not an option, the subject will be followed for 1 month post-explant and then withdrawn from the study. Subjects who undergo a revision or replacement procedure will resume their previous follow-up schedule.

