## Clinical Investigational Plan

inferiority between the DRG stimulation group compared to the SCS group with a pre-specified 10% non-inferiority margin. The study met the primary endpoint with statistically significantly more treatment successes in the DRG stimulation group compared to the SCS group at 3 months post permanent implant (81.2% vs. 55.7%, respectively;  $p = 0.0004$ ). This effect persisted at 12 months post implant (74.2% vs. 53.0%;  $p=0.0047$ ). Secondary and tertiary outcomes including percent change in VAS scores, change in SF-36 scores, change in Profile of Mood States (POMS) scores, and change in Brief Pain Inventory (BPI) scores were also suggestive of improvements in the group who received DRG stimulation compared to the SCS group.

The most commonly reported definitely-related adverse events (AEs) in the group who received DRG stimulation with the Axium Neurostimulator System in the ACCURATE IDE study were pain at the implantable pulse generator (IPG) pocket (14.5% of subjects) and loss of stimulation due to lead migration (11.8% of subjects). There were a total of 21 serious adverse events (SAEs) in 19 subjects reported in this study. The difference in overall rate of SAEs between the Axium and Control groups was not found to be statistically significantly different (Axium 10.5%, Control 14.5%,  $p=0.6248$ ). Additionally, the overall difference in the rate of SAEs during the system trial (Axium 1.3%, Control 3.9%,  $p=0.62$ ) and after the permanent implant (Axium 9.2%, Control 10.5%,  $p=1.0$ ) were not shown to be statistically significantly different. Only 1 serious adverse device effect (SADE; cardiac arrhythmia post-implant) was classified as possibly or definitely related to the device, procedure and/or stimulation in the group, which received the Axium Neurostimulator System. There were no reports of stimulation induced neurological deficits in either the control or Axium group at any point in the study.

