### 9.1.5 Serious Adverse Device Effect (SADE).

## 9.2 Assessing, Recording and Reporting AEs

Safety surveillance within this study and the safety reporting both performed by the investigator, starts as soon as the subject is consented for the study. The safety surveillance and the safety reporting will continue until the last investigational visit has been performed, the subject/investigator concludes his participation into the study or the subject/investigator withdraws the subject from the study, except as otherwise specified in the CIP.

Records related to the subject's subsequent medical course must be maintained and submitted (as applicable) to the Sponsor until the event has subsided or, in case of permanent impairment, until the event stabilizes and the overall clinical outcome has been ascertained. All AEs will be monitored until they are adequately resolved. The status of the subject's condition should be documented at each visit.

AE data will be collected throughout the clinical study and will be reported to the Sponsor on a dedicated case report form through the EDC system. Reportable events to sponsor are considered:

1. ***All SAEs (whether or not the event is device and/or procedure related)***
2. ***All procedure, device and/or stimulation-related AEs (whether or not the event is considered serious)***

Device, procedure, and stimulation-related AEs are defined as follows:

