## Clinical Investigational Plan

### 10.1 Primary Endpoint

The hypothesis is stated as follows:

$$H_0: p \geq 15.5\%$$

$$H_1: p < 15.5\%$$

where  $p$  is the 12-month SAE rate for subjects who receive the permanent Axium or Proclaim DRG IPG (proportion of subjects who experience at least one SAE from permanent implant through 12-month follow-up). The hypothesis will be tested at the 5% significance level. The analysis population will include subjects who received the permanent Axium or Proclaim DRG IPG, who either have an SAE after permanent implant or complete the 12-month follow-up visit.

The primary endpoint analysis will be conducted using Kaplan-Meier method on subjects who received the permanent Axium or Proclaim DRG IPG (primary analysis population). The serious adverse events (SAE) include adverse events which CEC adjudicates as serious events. The 12-month SAE rate will be estimated using Kaplan-Meier method with a 95% upper confidence bound (UCB) estimated using log-log transformation. If the 95% UCB is less than the 15.5%, the null hypothesis will be rejected.

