## Clinical Investigational Plan

2. If these attempts are unsuccessful, a letter should be sent to the subject's last known address or the subject's general practitioner (GP) and a copy of this letter should be maintained in the subject's medical records.

Note: If a subject misses one or more of the scheduled follow up visits (inclusive of the assigned visit windows) without being lost to follow-up this will be considered as a missed visit. The subject may, therefore, still return for subsequent visits and will not be withdrawn from the study.

If there is a potential withdrawal in the study, please contact a member of the study team to see if there is anything that can be done to keep the subject in the study.

An analysis will be performed to compare demographics and key clinical characteristics for the subjects who have withdrawn and those who continue to be enrolled in the study. This analysis will be reported in the annual progress reports.

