2.2.3 Survival Analyses

Survival analysis will be conducted to analyze the primary endpoint. Subjects without events will be censored at their last known event-free time point. Survival curves will be constructed using Kaplan-Meier estimates. The 95% confidence interval will be estimated using log-log transformation.

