2.3 Endpoint Analysis

2.3.1 Primary Endpoint

The hypothesis is stated as follows:

[REDACTED]

where p is the 12-month serious adverse event rate for subjects who receive the permanent Axium or Proclaim DRG IPG. The hypothesis will be tested at the 5% significance level.

The primary endpoint analysis will be conducted using Kaplan-Meier method on subjects who received the permanent Axium or Proclaim DRG IPG (primary analysis population). The serious adverse events include adverse events which occur after permanent implant and CEC adjudicates as serious events.

The primary endpoint includes all serious adverse events, including ones related to the neurostimulation device or procedure as well as any unrelated serious adverse events.

[REDACTED]

Statistical Analysis Plan

[REDACTED]

[REDACTED]

[REDACTED]

The 12-month (365 days) serious adverse event rate will be estimated using Kaplan-Meier method with a 95% upper confidence bound (UCB) estimated using log-log transformation. If the 95% UCB is less than the [REDACTED], the null hypothesis will be rejected.

[REDACTED]

[REDACTED]

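### New SAE collection stops one month after a final explant, although the primary endpoint counts every SAE to 12 months in all implanted subjects

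*Protocol*

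**What the plan says.** **Follow-up after explant.** Protocol 8.11 covers explants for any reason where re-implantation is not an option: "the subject will be followed for 1 month post-explant and then withdrawn from the study". Revised or replaced systems stay on the normal schedule. The synopsis lists only a 1-month safety call after such surgery, and only if necessary.

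**End of surveillance.** Protocol 9.2 runs safety reporting until the last visit, the end of participation, or the point where "the subject/investigator withdraws the subject from the study, except as otherwise specified in the CIP". Events already open are followed to resolution. No visible text uses the exception to collect new SAEs after an explant withdrawal.

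**Endpoint.** Protocol 10.1 defines the primary endpoint as at least one SAE between permanent implant and 12-month follow-up, tested against 15.5%. SAP 2.3.1 fixes the window at 365 days and counts related SAEs "as well as any unrelated serious adverse events".

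**Population and censoring.** Protocol 10.1 gives two populations. One is limited to implanted subjects "who either have an SAE after permanent implant or complete the 12-month follow-up visit". The other is analysed "using Kaplan-Meier method on subjects who received the permanent Axium or Proclaim DRG IPG (primary analysis population". SAP 2.2.3 adds: "Subjects without events will be censored at their last known event-free time point". Protocol 10.8 limits each endpoint to subjects with complete data and plans no imputation.

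**Withdrawals.** Protocol 13.0 promises to "compare demographics and key clinical characteristics for the subjects who have withdrawn and those who continue to be enrolled in the study". It does not ask about their later SAEs.

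**The concern.** Because unrelated SAEs count, a subject remains relevant to the endpoint after the device is removed. Collection nevertheless stops a month later, and what stops it is a clinical event rather than an administrative cut-off. Censoring then assumes that explanted subjects go on to have SAEs at the same rate as those still implanted, and nothing collected can test this. If their risk is higher, the rate reported to FDA is too low and the study passes too easily; if lower, the reverse.

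The two population statements in Protocol 10.1 add a separate ambiguity. The same event-free explanted subject is censored under one and dropped under the other. Dropping event-free subjects while keeping those with events pushes the rate up.

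**Working it through.** **1. Plan's own figures.** Protocol 5.0 plans 426 enrolled, 319 implanted and 287 analysed. The attrition rates are not in the visible text, but implied rates close the flow: 287/(1 − 0.10) = 318.9, rounded up to 319; 319/(1 − 0.25) = 425.3, rounded up to 426. Planned loss after implant is 32/319 = 10%.

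**2. Cut-off.** Observation of an SAE-free subject ends at min(12, explant month + 1). Unobserved time is 10 months for an explant at month 1, 8 at month 3, 5 at month 6, 2 at month 9 and 0 from month 11. It is approximate because visit windows are redacted and Protocol 8.10 counts from activation. With explants uniform over the year (assumed), 11/12 = 92% leave a gap, averaging 5.04 months over all explants.

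**3. Decision rule.** With S = 1 − x/n and se = √[x/(n(n − x))]/|ln S|, the bound is 1 − S^exp(1.645·se). For n = 319, 38 events give 15.27% (pass) and 39 give 15.61% (fail). The pass limit is 38/319 = 11.9%.

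**4. Inputs for size.** The base rate comes from the earlier randomised trial in Protocol 2.0: "after the permanent implant (Axium 9.2%, Control 10.5"%. Using 9.2%, the monthly hazard is λ = −ln(1 − 0.092)/12 = 0.00804. Assumptions not in the documents: final explants in e = 2.5%, 5% or 10% of implanted subjects, independent of SAEs and uniform over the year; SAE hazard after explant k times the base.

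**5. Subjects affected.** About 7, 14 or 28 SAE-free subjects per 319 leave early, each losing about 170 days. If half of explants already carry an SAE, read roughly one column to the left.

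**6. Kaplan-Meier bias.** To first order the shortfall is e × (k − 1) × λ × 5.04 × 0.908. At 10% and k = 2: 0.10 × 1 × 0.00804 × 5.04 × 0.908 = 0.37 points. Simulation (6,000,000 subjects per scenario, censored 30 days after explant) gives true rate / Kaplan-Meier estimate, %:

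| Hazard after explant | 2.5% explanted | 5% | 10% |
|---|---|---|---|
| 0.5x | 9.13 / 9.18 | 9.06 / 9.15 | 9.00 / 9.18 |
| 1x | 9.21 / 9.21 | 9.20 / 9.21 | 9.18 / 9.17 |
| 2x | 9.29 / 9.21 | 9.40 / 9.23 | 9.61 / 9.26 |
| 4x | 9.49 / 9.24 | 9.81 / 9.32 | 10.37 / 9.40 |

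First SAEs missed per 319, in the same column order: 0.3 / 0.6 / 1.2 at 1x, 0.6 / 1.2 / 2.3 at 2x, 1.1 / 2.2 / 4.3 at 4x.

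**7. Effect on the decision.** Chance of passing when the true rate is exactly 15.5% (n = 319, 20,000 runs), 8.11 rule / full follow-up, %:

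| Hazard after explant | 5% explanted | 10% explanted |
|---|---|---|
| 0.5x | 3.6 / 4.0 | 3.2 / 4.2 |
| 1x | 4.7 / 4.5 | 4.3 / 4.0 |
| 2x | 6.0 / 4.4 | 7.1 / 4.1 |
| 4x | 8.2 / 4.2 | 15.2 / 4.2 |

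**8. Restricted population.** At equal hazard the expected rate is [(1 − e)p + e·a] / [(1 − e) + e(a + b)]. Here a ≈ 0.054 is the chance that an explanted subject has an SAE while observed, and b = 0.908/12 = 0.076 the chance of reaching month 12 SAE-free. At e = 5%: (0.0874 + 0.0027)/(0.95 + 0.0065) = 9.42%, against a true 9.2%. At e = 10% it is 9.66%. Simulation gives rises of 0.1, 0.2 and 0.5 points at 2.5%, 5% and 10%.

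**The case against.** The strongest reply is that nothing is broken. The explant rule and the censoring rule fit together, Kaplan-Meier is standard for unequal follow-up, and bias is zero at equal risk. The large figures need extreme inputs: 10% final explants would use up all planned attrition, and no source supports a fourfold hazard. The earlier trial reported only one serious event related to device, procedure or stimulation in its Axium group, which suggests mostly background events and favours scenarios near 1x. This stands, and it is why the point is no more than something to consider.

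The SAE definition in Protocol 9.1.3 is visible only in part. If an explant, or the complication behind it, is adjudicated serious, that subject is already an event and has no gap. This also stands: the number affected cannot be given.

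Protocol 5.2 and SAP 2.1.1, 2.9, 2.13 and parts of 2.3.1 are redacted and may justify the rule or bound its effect. They may, but they cannot supply SAEs that were never collected.

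Following open events under 9.2 helps only with those events. The population conflict is a distinct issue that touches any event-free dropout, so it should be judged separately and adds no weight to the explant point.

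**Conclusion.** The concern holds. As written, new SAE collection ends one month after a final explant, and SAE-free subjects explanted before about month 11 contribute an assumption, not data, to the rest of the window. Size and direction of the bias are unknown. At 2.5% to 5% explanted and up to double the hazard it is at most 0.2 points, small against the distance from 9.2% to the 11.9% pass limit. It becomes material only with frequent explants and a risk several times higher, such as a 15.2% false-pass rate at 10% and fourfold, which no visible text supports or excludes. All of this rests on the assumed explant rates, uniform timing and independence from earlier SAEs.

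The conflict within Protocol 10.1, and with 10.8, needs no assumption to establish. The restricted population is wrong if followed, because it removes event-free subjects selectively and inflates the rate.

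**What to change.** **Data collection.** Amend Protocol 8.11 so that, with the subject's agreement, SAE-only contact by telephone or telemedicine continues at the remaining scheduled time points to 12 months after permanent implant. Invoke the exception in 9.2, and state that these SAEs count in the primary analysis. Remote visits are already allowed under 8.10, and explant decisions and care are untouched.

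*Cost.* At most three contacts (months 3, 6, 12). Under uniform timing, explants in months 0–2, 2–5 and 5–11 need 3, 2 and 1, so the mean is (2×3 + 3×2 + 6×1)/11 = 1.6. That is roughly 11, 23 or 46 calls in total at 2.5%, 5% or 10% explanted. The larger burden is the amendment itself: IRB notification or approval, and new signed consent under Protocol 15.0, potentially for up to 319 implanted subjects at up to 45 sites. Subjects already withdrawn may not be recovered. No enrolment or procedures are added.

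**Wording.** In Protocol 10.1 keep Kaplan-Meier on all implanted subjects, as SAP 2.3.1 does, and delete the restriction to subjects with an SAE or a completed 12-month visit. State that the complete-data rule in 10.8 does not apply to the primary endpoint. This needs no new data and no added contacts.

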### **8.12 Unscheduled Visits**

An unscheduled visit is defined as any visit that occurs outside of a specified study visit. Only unscheduled visits occurring after the permanent implant will be recorded. Examples of unscheduled visits may include subjects returning to the office for an AE or programming change.

## Clinical Investigational Plan

Table 1: List of all study specific activities/procedures

[REDACTED] if applicable

### 8.13 Validated Questionnaires

All validated questionnaires should be completed prior to reprogramming as applicable. The Study Coordinator or designee will give the subject the questionnaires to complete on his or her own. It is important that the subject understands the meaning of all the words in the questionnaires. The subject should be instructed to ask any questions about the questionnaires if further explanation is needed. Once the subject has completed the questionnaire, the Study Coordinator or designee will review the questionnaire for completeness to verify that all questions have been answered and only one response is chosen for each item.

#### Visual Analog Scale (VAS) for Pain

The VAS is a common, self-administered measure in which subjects rate their pain intensity by marking a vertical line through a 100 mm horizontal line anchored by word descriptors on each end (no pain to worst imaginable pain). The distance between the beginning of the horizontal line and the vertical line is measured to produce a score between 0 and 100 mm (or 0 to 10 cm). A higher score indicates higher pain intensity and a 30% reduction in VAS score from baseline to follow-up is considered clinically relevant. VAS scores for overall pain intensity will be collected.

#### Numeric Rating Scale for Pain (telemedicine visits)

The pain NRS consists of 1 question that will be asked by interviewing the subjects. Patients will be asked to rate, from 0 (no pain) to 10 (worst imaginable pain), their average pain over the past 24 hours specific to the area(s) of chronic pain being treated. A higher score indicates greater pain intensity

#### Neuropathic Pain Scale (NPS)

The NPS is a self-administered validated questionnaire designed to assess pain qualities and symptoms associated with neuropathic pain. The questionnaire is comprised of 10 scales which assess two global pain domains (pain intensity and unpleasantness), six specific pain qualities (sharp, dull, sensitive, hot, cold, and itchy pain), and two spatial qualities (deep and surface pain). Respondents rate the intensity or severity of each descriptor item on a scale from 0 to 10, where 0 represents no intensity/severity and 10 represents the most intensity/severity. The questionnaire takes 5 minutes to complete and yields scores for each pain quality/symptom as well as an overall mean score for all 10 scales. The NPS can be used to differentiate neuropathic pain from non-neuropathic pain. Mean scores of 5.5 or greater reflect presence of neuropathic pain whereas those below 5.5 reflect non-neuropathic pain.

#### PROMIS-29 Profile v2.0

The PROMIS-29 Profile is an instrument made up of seven individual short forms (physical function, anxiety, depression, fatigue, sleep disturbance, ability to participate in social roles and activities, pain interference) that are scored individually. The instrument also includes a single

[REDACTED]

[REDACTED]

## Clinical Investigational Plan

pain intensity item which is reported as its raw score (e.g., 0 to 10). Each item has five response options ranging in value from 1 to 5, except for the Pain Intensity item which has eleven response options ranging in value from 0 to 10. A raw score is created from each short form that makes up the Profile. Raw scores are calculated by summing the values of the response to each question within each domain. For example, for the 29-item Profile, the lowest possible raw score within anxiety is 4 (a score of 1 on all four items); the highest possible raw score is 20. Raw scores are converted into t-scores, where higher scores represent more of the concept being measured (i.e. physical function). For the depression, anxiety, physical function, pain interference, fatigue profile domains, a t-score of 50 is the average for the US general population with a standard deviation of 10. For the Ability to Participate in Social Roles and Activities and Sleep Disturbance profile domains, a score of 50 represents the average of a calibration sample, which generally contained more individuals with chronic illness. Thus, a score of 50 likely represents somewhat sicker people than the general population.

### PROMIS Global Health Version 1.1

The PROMIS Global Health short form is a validated, 10-item instrument designed to assess multiple health domains. The questionnaire yields a total score and sub-scale scores for Global Physical and Mental Health. Each question has potential five response options ranging in value from one to five to give a total score ranging from 10 to 50. All questions must be answered to arrive at a total score as one or more missing responses will render scores unusable. Scores are converted into t-scores where the average for the general US population is 50 and the SD is 10. Higher scores indicate better global health.

### Patient Global Impression of Change (PGIC)

The PGIC is the most commonly used patient-reported, anchor based method of assessing clinically important change. The PGIC consists of one question to assess change in activity limitations, symptoms, emotions, and overall quality of life related to their condition rated on a seven-point Likert scale. PGIC values of 6 or more are reported to correlate best with actual change.

## **8.14 Study Conclusion**

When the subject's participation in the clinical study has been completed, the subject will return to medical care as per their physician's recommendation. The study will be concluded when all sites are closed and the final report generated by St. Jude Medical has been provided to sites or St. Jude Medical has provided formal documentation of study closure.

## **9.0 ADVERSE EVENTS**

### **9.1 Definitions**

#### **9.1.1 Medical Device**

Any instrument, apparatus, machine, appliance, implant, software, material or other similar or related article intended by the manufacturer to be used, alone or in combination, for human beings for one or more of the specific purpose(s) of:

- Diagnosis, prevention, monitoring, treatments or alleviation of disease,
- Diagnosis, monitoring, treatment, alleviation of, or compensation for, an injury,
- Investigation, replacement, modification, or support of the anatomy or of a physiological process,
- Supporting or sustaining life,

## Clinical Investigational Plan

- Control of conception,
- Disinfection of medical devices and
- Which does not achieve its primary intended action in or on the human body by pharmacological, immunological or metabolic means, but which may be assisted in its intended function by such means.

### 9.1.2 Adverse Event (AE)

Any untoward medical occurrence, unintended disease or injury, or untoward clinical signs (including abnormal laboratory findings) in subjects, users or other persons, whether or not related to the medical device under study. This definition includes events related to the medical device and to the procedures involved.

